16.0 Archiving

Site files will be stored in the locked research room at Perth Hip and Knee Subiaco. As per the NHMRC code, data will be stored for 15 years. Patient information will be located on Genie Medical Solutions software, and on research database Socrates. Both of this software programs are located on servers within Australia, and are automatically back up. These programs can only be accessed by login and password, and are located on computers at Perth Hip and Knee Clinic.

17.0 Publication and Dissemination Policy

The findings of this study will be published in peer-review journals. There are no terms or conditions to the funding that may impact upon publication and dissemination. Authorship will reflect the amount of time spent designing the study, collating the data and writing the manuscript.

19.0 Appendices

Appendix 19.1 : Patient Case Report Forms

Patient ID :

Preop

1. Relevant Past Medical History

2. Previous Surgery to knee (including dates)

3. Other relevant notes in history

4. Additional future elective surgery planned

5. Current Medication and Analgesia Regime

PROMS

- Oxford
- Forgotten joint
- Kujala
- Eq5D-5L
- Vas Pain
- Koos JR

Functional

- Range
- Mobilisation Equipment
- Lachmeter
 - 90*
 - 20*
- Dynamometer
 - Knee flexion (achillies)
 - Knee extension (Anterior distal shin)
- 30STS
 - Mods?

Completed by :

6 weeks

1. Current Medication and Analgesia Regime

2. Hospital Admission since last visit - if need be, complete SAE.

3. How satisfied are you with your knee replacement?

0 Extremely satisfied 0 Satisfied 0 Neutral 0 Dissatisfied 0 Extremely Dissatisfied

PROMS

- Forgotten joint
- Vas Pain

Functional

- Range
- Mobilisation Equipment
- Dynamometer
 - Knee Flexion (Achille's)
 - Knee Extension (Anterior distal shin)

Physio Observations and Treatment plan

3. Protocol Deviation and reason why

Completed by :

3 Months

1. Current Medication and Analgesia Regime

2. Hospital Admission since last visit - if need be, complete SAE.

3. How satisfied are you with your knee replacement?

0 Extremely satisfied 0 Satisfied 0 Neutral 0 Dissatisfied 0 Extremely Dissatisfied

PROMS

- Oxford
- Forgotten joint
- Kujala
- Eq5D-5L
- Vas Pain
- KOOS Jr.

Functional

- Range
- Mobilisation Equipment
- Lachmeter
 - 90*
 - 20*
- Dynamometer
 - Knee Flexion (Achillies)
 - Knee Extension (Distal anterior shin)
- 30STS
 - Mods?

- XRAY (A/P, lat, skyline and LLWB)

3. Physio Observations and Treatment plan

4. Protocol Deviation and reason why

Completed by :

12 Months

1. Current Medication and Analgesia Regime

2. Hospital Admission since last visit - if need be, complete SAE.

3. How satisfied are you with your knee replacement?

0 Extremely satisfied 0 Satisfied 0 Neutral 0 Dissatisfied 0 Extremely Dissatisfied

PROMS

- Oxford
- Forgotten joint
- Kujala
- Eq5D-5L
- Vas Pain
- KOOS Jr.

Functional

- Range
- Mobilisation Equipment
- Lachmeter
 - 90*
 - 20*
- Dynamometer
 - Knee Flexion (Achillies)
 - Knee Extension (Anterior distal shin)
- 30STS
 - Mods?

- XRAY (A/P, lat, skyline)

3. Physio Observations and Treatment plan

4. Protocol Deviation and reason why

Completed by :

24Months

1. Current Medication and Analgesia Regime

2. Hospital Admission since last visit - if need be, complete SAE.

3. How satisfied are you with your knee replacement?

0 Extremely satisfied 0 Satisfied 0 Neutral 0 Dissatisfied 0 Extremely Dissatisfied

PROMS

- Oxford
- Forgotten joint
- Kujala
- Eq5D-5L
- Vas Pain
- KOOS Jr.

Functional

- Range
- Mobilisation Equipment
- Lachmeter
 - 90*
 - 20*
- Dynamometer
 - Knee Flexion (Achillies)
 - Knee Extension (Anterior distal shin)
- 30STS
 - Mods?

- XRAY (A/P, lat, skyline)

3. Physio Observations and Treatment plan

4. Protocol Deviation and reason why

Completed by:

Please complete end of study form.

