3.6 Randomisation procedure

The system for randomisation will be the same throughout the study period and must be strictly adhered to. The following method will be used to allocate a trial patient to either the mFA TKA ('Control group') or to the kFA TKA ('Investigation group').

Randomisation will be carried out using a blocked effect. This method is designed to randomize subjects into two groups that result in equal sample sizes over time. The blocks will be small (n=4), and balanced within the predetermined group assignments, which will keep the number of subjects in each group similar at all times. There will be no stratification factors involved in the randomization as randomization will occur before the trial starts. Using a randomization website (www.random.org), a random number (between 1 and 100000) will be generated. This will form the "seed" number for the blocked randomization process. Using a randomization website (www.sealedenvelope.com) the randomization list will be created. Patients will be allocated in a sequential order of consent, strictly adhering to the allocation of groups. Screen shots of the randomization process and seed number will be taken throughout, and held from the CI to minimize randomization bias. The orthopedic fellow will then privately communicate to the CI the allocated group, to enable alignment and templating planning to be performed using the MAKO software. All patients and clinical staff recording the post operative clinical outcomes of interest will remain blinded to minimize performance and detection bias.

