3.10 Clinical and radiological assessment

The FJS, EQ5D-5L, OKS, VAS Pain, Likert scale, KOOS Jr and Kujala Anterior knee pain scores are validated tools for the clinical assessment of patients after knee arthroplasty (10,11,18,19). Each of these scores is completed preoperatively and then at regular intervals during follow-up (Appendix 19.1). This information is routinely discussed at each of these outpatient consultations but patients in this study will have the information recorded within these validated questionnaires to facilitate data analysis.

Routine clinical measures of height, weight, range of movement and pain description will be taken. To test endurance and strength, a 30 sec Sit to stand test will be measured. This test asks the participant to stand up / sit down from a standardised chair height within 30 seconds (Appendix 19.6). To measure the AP stability of the knee (20), a lachmeter reading will also be recorded at the post operative intervals and to measure strength, a hand

held dynamometer test will also be performed.

	Preoperative	Discharge	6 weeks	3 months	1 year	2 years
Patient demographics	X					
Patient medical history	X					
Operation details		X				
Clinical history and PROMS (FJS, EQ5D-5L, OKS, VAS pain, KOOS Jr, Kujala Anterior Knee Pain, Likert scale)	X		X (FJS and VAS only)	X	X	X
Functional Examination (Lachmeter testing, Range of Movement, Hand Held Dynamometer, 30s STS test)	X	X (range only)	X (range only)	X	X	X
Adverse Events	At occurrences through study period					

Table 1. Timelines for clinical data collection in all study patients.

	Preoperative	Discharge	6 weeks	3 months	1 year	2 years
Plain knee joint radiographs	X	X			X	X
Plain long-leg radiographs	X			X		
CT Knee joint	X					

Table 2. Timelines for radiological data collection in all study patients. Assessment windows will be as followed; 6 weeks review (± 1 week), 3 month review (± 2 weeks), 12 month review (± 2 months), 2 year review (± 2 months).

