14.2 Reporting Incidents involving a medical device

Adverse device effects (complications) are defined as any of the following:

- a) Any device component failure (e.g. excessive migration of the implant or failure otherwise).
- b) Local complications arising from use of the TKA implants to include osteolysis, inflammation, local tissue reaction, periprosthetic fracture.
- c) Bone fracture during implantation
- d) Nerve damage arising from implant placement (as evidenced immediate postoperative by motor and/or sensory deficit not present preoperatively).
- e) Large vessel damage arising during surgery (with large blood loss, i.e. > 1500 ml).
- f) Prosthetic joint infection
- g) Surgical site infection
- h) Loosening of prosthetic components
- i) Other adverse events that are deemed device related and serious.

All serious adverse events, life-threatening problems, or deaths that occur during or following the use of the devices during the study should be fully documented in the research record by the Chief Investigator including the onset date, complete description of the event, severity, duration, action taken, and outcome. The event should be documented at the appropriate interval case report form. The Chief Investigator will be responsible for notifying the reviewing Research Ethics Committee, of any unanticipated adverse events according to local regulations.

The Chief Investigator will record all non-serious adverse events on the appropriate case report form.

Some adverse events may lead to subsequent surgical intervention. The surgical intervention should be reported separately from the presentation of the other adverse event. For example, if the adverse event is reported at the 3 months visit and a revision subsequently occurs after the 3 months visit, the revision should be reported in the next follow-up visit.

In the short term, revisions will usually occur due to acute/chronic infection, instability, and/or subject experiencing severe pain due to various causes. This data will be used in combination with clinical assessment, target history / examination and further investigation to determine likelihood of requiring revision.

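### No case report form has a field for adverse events or section 14.2 complications, so complications that are not serious and need no admission rely on unprompted recording by the unblinded Chief Investigator

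*Combined protocol and SAP*

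**What the plan says.** Section 14.2 introduces a list, (a) to (i), with "Adverse device effects (complications) are defined as any of the following". It covers device failure, local reactions, intraoperative injury, nerve damage, infection and loosening. The section then sets two recording rules. For serious events, "The event should be documented at the appropriate interval case report form". For the rest, "The Chief Investigator will record all non-serious adverse events on the appropriate case report form". Table 1 in section 3.10 schedules adverse events as "At occurrences through study period", with no visit attached.

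The postoperative forms in Appendix 19.1 cover medication and analgesia, admission, satisfaction, PROMs, function, physiotherapy notes and protocol deviations. The event prompt on each is "Hospital Admission since last visit - if need be, complete SAE". Each also has a free-text line, "Physio Observations and Treatment plan". The forms from 3 months on list the films to be taken; at 3 months the line reads "XRAY (A/P, lat, skyline and LLWB".

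On blinding, section 3.6 states: "The orthopedic fellow will then privately communicate to the CI the allocated group". Section 3.9 has blinded observers record the outcomes of interest at follow-up.

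**The concern.** The recording rule in section 14.2 assumes forms that can hold adverse events, and the forms supplied cannot. A complication handled in clinic prompts no question. If it is not serious, the person named to record it knows which operation the patient had. Two problems follow. Events may be missed because nobody is required to ask, and the chance of being recorded could differ between arms because the recorder is not blinded.

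Section 1.2 explains why this matters. It says that a move away from mechanical alignment needs justification because functional alignment has no long-term longevity data, and that surgeons and patients need the risks and benefits defined. Complications are not among the objectives in sections 2.1 and 2.2, so this concerns the safety description, not the primary endpoint.

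**Working it through.** The plan gives no figure to reproduce, so the check sets the recording rule against the forms field by field.

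**1. Fields on the four postoperative forms (6 weeks, 3, 12 and 24 months), Appendix 19.1**

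| Field | Forms with it |
|---|---|
| Hospital admission prompt, leading to the SAE form | 4 of 4 |
| Adverse-event or complication field | 0 of 4 |
| Free-text physiotherapy line | 4 of 4 |
| Radiograph line | 3 of 4 |
| Field for radiographic findings | 0 of 4 |

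**2. Other forms.** The intraoperative form (19.8) records alignment, gaps, soft tissue releases, patellar tracking and femoral bone loss, but has no complication field. The end of study form (19.2) records death and implant removal only as reasons for ending follow-up. Table 1 has a discharge column and section 3.9 a review at 2-3 weeks; Appendix 19.1 contains no form for either.

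**3. Where each section 14.2 item would surface**

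- (c) fracture during implantation and (e) large vessel damage occur in theatre, so they belong on form 19.8.
- (d) nerve damage is defined as evident immediately after surgery, so it belongs on form 19.8 or at discharge.
- (a) migration, (h) loosening and the osteolysis part of (b) are largely radiographic. Films are listed, but nothing on the form asks what they show.
- (f) joint infection and periprosthetic fracture in (b) would usually lead to admission (my assumption) and so meet the existing prompt.
- (i) is limited to serious events, which have the SAE route.
- (g) surgical site infection when superficial, and the inflammation and local tissue reaction in (b), can be managed without admission. No prompt reaches them.

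**4. Who records the remainder.** Under Table 3 in section 12.1, an event is serious if it causes death, threatens life, requires or prolongs hospitalisation, causes lasting disability or is a congenital anomaly. A complication meeting none of these is non-serious. Section 14.2 gives it to the CI, and section 3.6 tells the CI the arm.

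**5. Scale.** Section 3.5 enrols 100 patients 1:1, so 100 / 2 = 50 per arm. Each unrecorded patient event lowers that arm's observed proportion by 1/50 = 2 percentage points. How many would go unrecorded, and whether more in one arm, cannot be derived: the documents give neither complication rates nor recording rates.

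**The case against.** A reader might infer that these complications are captured only if the CI happens to note them. The documents do not support that.

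- Recording every non-serious event is a stated duty of the CI, and Table 1 plans collection throughout the study.
- Events that are serious without admission go through the SAE form, the medical records and the site's AE log (section 14.0 on recording serious adverse events).
- Section 10.0 lets any delegated staff member complete forms. A blinded observer could write an infection in the physiotherapy line, or it might show up under current medication.
- Appendix 19.4 is headed as a form for both SAEs and AEs and accepts an outcome of other.

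All of this stands, but none of it supplies a question put to every patient. Table 1 fixes timing only. A blank free-text line cannot be read as no event. Appendix 19.4 is laid out as a report to the ethics committee on serious or unexpected events, and section 14.0 invokes it for SAEs.

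A second tempting reading is that the visit forms miss all of items (a) to (i). They do not: some items are intraoperative or immediately postoperative, and others are caught by the admission prompt.

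A third is that complications will be under-counted in one arm. The documents show the opportunity for that, not its occurrence; any numerical split would only return the recording rates assumed.

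Finally, the adverse-event text in this copy has gaps: the causality section resumes mid-sentence, and an outcomes subsection in the contents does not appear. Another capture route may be described there. The visit forms themselves run without a visible break.

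**Conclusion.** The concern holds in this form: section 14.2 directs events to case report forms that have no place for them. Complications that are not serious and need no admission depend on unprompted recording assigned to someone who knows the allocation. The affected group is narrow: mainly superficial surgical site infection and local reaction or inflammation, with loosening or osteolysis seen on film but not leading to admission.

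Ascertainment may be incomplete and could differ by arm, by an amount the documents do not allow to be quantified. The conclusion rests on the forms as reproduced in Appendices 19.1 and 19.8 being complete, and on no systematic adverse-event question existing in text missing from this copy. The primary analysis is unaffected. The point is still worth acting on, because an event not asked about at the visit may not be recoverable later and the remedy is cheap.

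**What to change.** 1. Add to each of the four postoperative forms a fixed yes/no-and-date item for complications since the last visit that a patient can report or an examiner can see. Ask it of every patient in both arms.
2. Have it asked by an assessor who is blinded and took no part in randomisation. This needs stating: section 3.4 has the fellow randomise, section 5.0 has the Research Physiotherapist do so, and section 3.9 has both assist at follow-up.
3. Add a findings field (loosening, migration, osteolysis, fracture) to the radiograph line on the 3-, 12- and 24-month forms. Patients cannot report these.
4. Record fracture during implantation, vessel damage and nerve deficit on form 19.8 or at discharge; the latter needs a discharge page.
5. Keep CI reporting, the SAE form and the AE log as additional routes, and state how the new items link to them.
6. Tabulate events by randomised arm. Section 6 does not mention adverse events, so this is an addition.

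The cost is a short block on existing forms and about a minute per visit, with no new visit or procedure.

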Appendix 19.2 – End of Study Form

END OF STUDY FORM**RCT: MAKO mFA TKA vs MAKO kFA TKA**

Name (Initials only)	Study Number:	 M  F	DOB:
Date of form completion			
Years since operation			
Classification	 Reached end of follow-up		
	 Complete withdrawal from study		
	Reason (if given):		
	 Withdrawal from study apart from survivorship analysis		
	Reason (if given):		
	 Lost to follow-up		
	 Death		
 Implant removed			
If withdrawn from study, does patient agree to be contacted annually for survivorship analysis?			
Comments			
Signature of PI:			
Date:			

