3.9 Post operative follow up

All patients included in this study will undergo orthopaedic review at the PHK Clinic or Midland Orthopaedic Clinic at 2-3 weeks, 6 weeks, 3 months, 1 year and 2 years following surgery. These are the routine follow-up time intervals for non-study patients undergoing TKA at PHK. Clinical and radiological outcomes of interest will be recorded by blinded observers using case report forms during these follow-up times (Appendix 19.1). The RP and fellow will assist in this.

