4.2 Patient withdrawal criteria and procedure

All patients included into this study are free to withdraw from the study at any time without compromise to their future treatment. On withdrawal, patients will revert to the standard follow-up regimen for routine TKAs at the study site. The end of study form will be completed and the reason for withdrawal documented (Appendix 19.2). This form will also be completed if the patient is lost to follow-up or dies during the course of the study.

Enrolled patients will be withdrawn from the study if:

- The patient withdraws consent for participation in the study
- The patient is no longer able to comply with study instructions, attend scheduled appointments or complete questionnaires
- The patient undergoes implant revision

Data to the point of withdrawal will be used for analysis.

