5.1 Eligibility Criteria

The inclusion and exclusion criteria for all patients included in this study is shown below:

Inclusion Criteria

- Patient has symptomatic knee osteoarthritis requiring primary TKA
- Patient and surgeon are in agreement that TKA is the most appropriate treatment
- Patient is fit for surgical intervention following review by surgeon
- Patient is between 45-75 years of age at time of surgery, computer literate, and able to complete patient reported outcome measures independently.
- Patient must be capable of giving informed consent and agree to comply with the postoperative review program
- Patient must be a permanent resident in an area accessible to the study site
- Patient must have sufficient postoperative mobility to attend follow-up clinics and allow for radiographs to be taken
- Patient has tried non-pharmacologic therapy's including ; patient education, self-management programs, aerobic exercise, weight loss, physiotherapy and occupational therapy
- Patient has tried appropriate pharmacologic therapies including ; regular paracetamol and NSAIDS if appropriate

Exclusion Criteria

- Patient is not suitable for routine primary TKA. E.g. patient has ligament deficiency that requires a constrained prosthesis
- Interoperative requirement for a more constrained implant.
- Intraoperative requirement for the PCL to be released. These patients will be still included in the study, but analyzed with an intention to treat principal.
- Patient has bone loss that requires augmentation
- Patient requires revision surgery following previously failed correctional osteotomy or ipsilateral TKA (eg. Post high tibial or distal femoral osteotomy)
- Patient requires a polyethylene inset of 16mm or greater.
- Patient is immobile or has another neurological condition affecting musculoskeletal function
- Patient is less than 44 years of age or greater than 76 years of age
- Patient is a compensable patient. I.e. Worker's compensation claim or motor vehicle accident.
- Patient is already enrolled on another concurrent clinical trial
- Patient is unable or unwilling to sign the informed consent form specific to this study
- Patient is unable to attend the follow-up program
- Patient is non-resident in local area or expected to leave the catchment area postoperatively
- Patients who lacks capacity to provide consent, or the ability to understand the study protocol due to a cognitive condition (eg. Dementia)

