6.3 Intention-to-treat population

The intention-to-treat (ITT) population is defined as all randomised patients assigned to either the mFA TKA or kFA TKA group, regardless of adherence with the entry criteria, regardless of the treatment they actually received, and regardless of subsequent withdrawal from treatment or deviations from the protocol. In the event that MA is converted to FA or vice versa intraoperatively, analysis will be performed using the ITT population and the treatment actually received by the patients. Intra-operative conversion from one method to another will however, be documented and presented/ published as part of the study.

In the event that there are errors in the randomization assignment, the analysis will be performed using the assigned treatment, not the treatment that the patient actually received. Any patient terminated early from the clinical trial will be included in the ITT population. All attempts will be made to collect complete follow-up evaluations for these patients despite study exit. These patients will be included in the analysis using univariate or multivariate-imputation methods.

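### The End of Study form and section 4.2 do not carry out section 6.3's promise of follow-up after study exit, so willing patients' two-year FJS may go uncollected or unused

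*Combined protocol and SAP*

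**What the plan says.** The End of Study form (Appendix 19.2) has two boxes for a patient who decides to stop: "Complete withdrawal from study" and "Withdrawal from study apart from survivorship analysis". Each has space for a reason. The other boxes cover reaching the end of follow-up, loss to follow-up, death and implant removal. The only question about later contact is "If withdrawn from study, does patient agree to be contacted annually for survivorship analysis". There is also a free-text comments field.

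Section 4.2 describes what follows: "On withdrawal, patients will revert to the standard follow-up regimen for routine TKAs at the study site". On the data it says: "Data to the point of withdrawal will be used for analysis".

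Section 6.3 places anyone who leaves early in the ITT population and states: "All attempts will be made to collect complete follow-up evaluations for these patients despite study exit". It adds that imputation will be used to include these patients in the analysis.

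Three other places bear on feasibility. Section 3.9 says of the study's visit times: "These are the routine follow-up time intervals for non-study patients undergoing TKA at PHK". Section 5.1 requires patients to be "computer literate, and able to complete patient reported outcome measures independently". Section 3.10 says the topics are discussed routinely at outpatient visits, but describes recording them in the questionnaires for study patients.

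**The concern.** The point concerns patients who choose to stop. It does not concern the rules in section 4.2 that withdraw patients after revision or when they can no longer comply.

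A patient may tire of the study visits, which include arthrometer, dynamometer and sit-to-stand testing, and still be willing to fill in a 12-item questionnaire at two years. The form has no place to record that. The permission it does seek serves survivorship, which appears neither among the objectives in section 2 nor among the endpoints in section 6. The two-year FJS, on which the trial turns, is not mentioned.

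Section 4.2 points the same way as the form and section 6.3 points the other way. Staff who follow the form and section 4.2 would have no prompt to ask for the two-year FJS. If a value were collected anyway, section 4.2 makes no provision for analysing it. At stake is the ITT analysis, which is the plan's check on a primary analysis restricted to patients who complete the study (sections 6.2.1 and 6.4). That check is weaker if it relies on imputation where observed values could have been had.

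**Working it through.** **Step 1. The texts side by side, for a patient who stops voluntarily**

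| Question | Form (19.2) | Section 4.2 | Section 6.3 |
|---|---|---|---|
| Is follow-up continued? | Survivorship contact only, if agreed | Routine care | Full evaluations sought |
| Is agreement to give the FJS requested? | No | Not mentioned | Implied, no mechanism given |
| Are later data analysed? | Not applicable | Data up to withdrawal | Patient kept in ITT, with imputation |

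The form and section 4.2 agree with each other, and neither supplies what section 6.3 needs.

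**Step 2. Does routine care fill the gap?** Not by itself. Section 3.9 puts routine visits at the study's time points, so a withdrawn patient may well attend at two years. Section 3.10, however, describes questionnaire recording for study patients. A withdrawn patient could be seen at two years without an FJS being taken. The visit is an opportunity to collect the score, not an arrangement to do so.

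**Step 3. The plan's own retention figure.** Inputs: 90 patients required and 100 enrolled (section 3.5); 10% drop-out (section 6.1).

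90 / (1 − 0.10) = 100, which reproduces the stated enrolment. Expected drop-outs are 100 × 0.10 = 10.

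**Step 4. Which analysis would gain?** Section 6.4 limits the per-protocol set to patients who complete the study as the protocol lays down. Someone who stops visits and functional tests but returns the FJS would not qualify. Any gain is therefore in the ITT analysis.

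**Step 5. Illustrations, ITT only.** The documents do not say how many of the 10 would be voluntary stoppers or how many of those would continue with questionnaires. Let k be the number who do both. With equal arms and a common SD, the standard error of the difference in observed means is proportional to 1/√N, so the ratio to the case with 90 observed values is √(90/(90 + k)):

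- k = 1: √(90/91) = 0.994, a fall of about 0.6%
- k = 5: √(90/95) = 0.973, a fall of 2.7%
- k = 10, the ceiling: √(90/100) = 0.949, a fall of 5.1%

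For bias, suppose a fraction m is missing in each arm, and let D be the between-arm difference in how far leavers fall below completers. An analysis that treats leavers as if they resembled completers is off by m × D. The values of D below are assumptions, set at one and two times the 12-point target in section 6.1; the documents give no source for them.

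- m = 0.10: 0.10 × 12 = 1.2 points and 0.10 × 24 = 2.4 points
- m = 0.05: 0.05 × 12 = 0.6 points and 0.05 × 24 = 1.2 points

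Moving from 0.10 to 0.05 corresponds to k = 5, and halves the bias only if D is the same among those still missing.

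**The case against.** The strongest reply is that section 6.3 already commits the investigators to pursue follow-up, and a missing box does not cancel that commitment. The form is a status record signed by the principal investigator, with space for reasons and comments, and nothing in section 4.2 makes it the instrument of consent. This stands to an important extent. A reader might infer that the two-year FJS of these patients is certain to be lost. The documents do not support that: the values are at risk, because collection depends on staff acting on section 6.3 without a prompt.

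A reader might also infer that permission for contact after withdrawal is sought nowhere. That cannot be said either. The consent pages were not available for review and may contain it. The form would still not record what the patient agreed to.

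It can be said that the numbers are small and hypothetical. That is right. The 10 expected drop-outs also include patients lost to follow-up, deaths and implant removals, so recovering 5 of them is not something the documents support. Patients and outcome assessors are blinded (section 3.6), which makes large arm-specific differences among leavers less plausible. Nor is it fair to say that the sample has no reserve: the 10 patients enrolled beyond 90 are the reserve, and at the planned drop-out the target is met.

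Finally, the sentence in section 4.2 might be read as a minimum, since it does not say that later data are excluded. In a passage that has just returned the patient to routine care, the more natural reading is a limit. At best the text is ambiguous where section 6.3 is not.

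**Conclusion.** The point holds as a mismatch between the form and section 4.2 on one side and section 6.3 on the other. The form gives no means of agreeing to continue with the FJS, and section 4.2 provides for analysing data only up to withdrawal, against the follow-up and ITT inclusion promised in section 6.3. Two-year FJS values from willing patients are at risk of not being collected or not being used, which leaves the ITT analysis to rely on imputation.

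The size of the loss cannot be computed from the documents. The standard-error and bias figures above are ITT-only illustrations on stated assumptions. It would be tempting to read them as a gain in precision for the primary analysis, from 90 to 95 evaluable patients. The per-protocol definition in section 6.4 rules that out.

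This is a worthwhile and inexpensive correction that should be made. It does not undermine the primary analysis as planned.

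**What to change.** 1. **Form (Appendix 19.2).** Add a tier, separate from complete withdrawal: the patient stops study visits and functional tests but agrees to complete the FJS and other questionnaires, at least the two-year FJS, at routine review or remotely. Add a matching permission line that is distinct from the survivorship question.
2. **Section 4.2.** Amend the sentence on data use so that data given with the patient's agreement after withdrawal are also analysed, in line with section 6.3. Changing the form alone would leave the conflicting sentence in place.
3. **Section 6.3.** State that patients in the new tier enter the ITT analysis with their observed values, and that imputation is kept for values that remain missing.

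The cost is one form revision and a sentence or two in each section, with some reminder effort and mixed clinic and remote completion for a few patients. The information sheet may need matching wording, to be checked against the consent documents.
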